6.3 Investigational Agent #3: Janssen COVID-19 Vaccine

The Janssen COVID-19 Vaccine (AD26.COV2.S) has not been a study-provided vaccine since 01/06/2022.

ACV01 Dose and Volume	5 mcg / 0.5mL	
ACV01 Number of Doses Per Vial	Multiple Dose Vial: 10 doses (After Mixing)	

6.5 Drug Accountability

Under Title 21 of the Code of Federal Regulations (21CFR §312.62), the investigator bears the responsibility to maintain adequate investigational product (IP) disposition records (receipt, storage, dispense, return, and destruction). DAIT/ NIAID requires the principal investigator(s) to delegate the IP disposition responsibility to a licensed/registered pharmacist at a registered investigational pharmacy at a clinical research site. Detailed information on investigational pharmacy requirements is provided in the DAIT Pharmacy Guidelines. All IP inventory and dispensing will be documented using a DAIT/ NIAID main accountability as well as participant-specific dispensing fillable PDF forms or

electronic logs that are 21 CFR 11 compliant and approved by DAIT/NIAID. The participant dispensing log(s) will be kept current and will contain the identification of each participant as well as the date and quantity of each IP prepared and dispensed. Detailed IP shipment records to each clinical site's investigational pharmacy will be maintained by the DAIT/NIAID's Clinical Product Center (EMINENT Services Corporation). All records regarding IP disposition will be available for inspection. All remaining unused IP will be returned to the IND Sponsor (DAIT/ NIAID) or sponsor's representative after study termination or destroyed with the prior approval from the sponsor in accordance with applicable federal and state laws as well as the study site procedures.

6.6 Assessment of Participant Compliance with Investigational Agent

Participants in this study will receive the assigned vaccine under direct observation.

6.7 Toxicity Prevention and Management

Participants will receive investigational agents in facilities where the investigative team is familiar and practiced in the treatment and care of participants with systemic autoimmune diseases and complications associated with those disorders and the associated treatments. Vaccinations will also only be given by personnel trained in recognizing and managing treatment of systemic allergic reactions and in areas equipped with the necessary medications and supplies to treat systemic allergic reactions. Participants who are experiencing a disease flare at Baseline/Week 0, or who meet any of the conditions listed in Section 8.1.3 Baseline (Week 0/Day 1) Visit will not proceed with vaccination. Refer to Section 5.1.1.1 Allergic Reactions and Anaphylaxis and Section 7.4 Rescue Medications.

7. Other Medications

7.1 Concomitant Medications

7.1.1 Protocol-mandated Medications

There are no protocol-mandated medications in this clinical trial. However, there is protocol-mandated temporary cessation as follows:

- Adult and Pediatric Stage 1 participants:
 - There will be a protocol-mandated temporary cessation of cohort-defining IS in **some** participants in Cohort A (MMF/MPA) and Cohort B (MTX).
- Adult and Pediatric Stage 2 participants:
 - There is a protocol-mandated temporary cessation of cohort-defining IS in **all** Cohort D (MMF/MPA) and Cohort E (MTX) participants.
 - Any participants in Cohort F (BCDT) who are also taking MMF/MPA or MTX will have a protocol-mandated temporary cessation of their MMF/MPA or MTX dose.

Adult and Pediatric Stage 1 in Cohort A: MMF/MPA and Cohort B: MTX that are randomized to hold these medications at the time of the additional homologous vaccine dose (per Section 3.1 Description of Study Design) and all Adult and Pediatric Stage 2 participants will be required to hold these medications as follows:

- Participants taking MMF/MPA (any dose) will hold the doses for 3 days before and 10 days after their vaccine dose.
 - Participants taking additional IS medications (such as tumor necrosis factor [TNF] inhibitors, JAK inhibitors, abatacept, belimumab, etc.) will be required to continue them during the time of the additional vaccine dose.
- Participants taking MTX (at any dose) will be required to hold their weekly dose for **at least 7 days before** their vaccine dose and for **at least 7 days after** administration of the vaccine. In total, the participant should not hold their MTX for more than 21 days.

- Participants taking additional IS medications (such as TNF inhibitors, JAK inhibitors, abatacept, belimumab, etc.) will be required to continue them during the time of their vaccine dose.

Participants that are randomized to continue medications (per Section 3.1 Description of Study Design) are required to maintain a stable dose of medication during the same period (Cohort A: MMF/MPA from 3 days before to 10 days after the additional homologous vaccine dose; Cohort B: MTX from 7 days before to 7 days after the additional homologous vaccine dose) unless they experience a change in disease activity requiring medication changes.

All participants in Cohort C: B-cell depleting therapy will continue to take their prescribed medications throughout the trial, unless they experience a change in disease activity requiring medication changes. It is preferred that these medications be stabilized before entry and continued wherever practical without variation of dose or regimen during the study.

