4.2.1 Inclusion and Exclusion Criteria for Adult Participants

4.2.1.1 Inclusion and Exclusion Criteria for Adult Stage 1

4.2.1.1.1 Inclusion Criteria for Adult Stage 1

Individuals who meet all of the following criteria are eligible for randomization/allocation as study participants in Adult Stage 1:

1. Individuals 18 years of age or older that meet classification criteria for SLE, SSc, RA, MS, or pemphigus.
2. Participants must meet the 2019 American College of Rheumatology/European League Against Rheumatism (ACR/EULAR) [2] or 2012 Systemic Lupus International Collaborating Clinics (SLICC) classification criteria for SLE [3], the 2010 ACR/EULAR classification criteria for RA [4], the 2013 EULAR/ACR classification criteria for SSc [5], the 2017 McDonald [6] criteria for MS, and the international consensus criteria for pemphigus [7].
 - a. If a participant has been diagnosed with more than one autoimmune disease, the participant will be assessed based on the disease that is selected for study entry.
3. Willing and able to sign informed consent.
4. Documented full COVID-19 vaccination (CDC card or documentation in medical records) that was completed at least 4 weeks prior and no more than 52 weeks prior to the Screening visit.
5. Negative or suboptimal serologic response to initial COVID-19 vaccine regimen, defined as an Elecsys® Anti-SARS-CoV-2 S result ≤ 200 U/mL, at Screening visit.
 - a. Initial COVID-19 vaccine regimen is defined as either:
 - i. 2 doses of the Pfizer-BioNTech COVID-19 Vaccine
 - ii. 2 doses of the Moderna COVID-19 Vaccine
6. Must be currently taking one of the following IS medications with or without additional disease-related medications: MMF (minimum of 1000 mg per day)/MPA (minimum of 720 mg per day), MTX (minimum of 7.5mg per week), or B cell depleting agents within the past 18 months (such as rituximab, ocrelizumab, or ofatumumab).

- a. If taking MMF/MPA or MTX, the participant must have initiated therapy at least 8 weeks prior to randomization and be taking the same medications (regardless of dose) as at the time of the initial COVID-19 vaccine regimen. Note: Participants who withheld their IS medications around their initial vaccinations are eligible to participate.
- b. If enrolling in the BCDT cohort, the participant must have received an anti-CD20 or an anti-CD19 BCDT in the past 18 months.

7. No changes in background IS medications, including MMF/MPA or MTX, in the 4 weeks prior to Screening, excluding the following:

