Together, the data assembled through these mechanistic studies will inform the community about the mechanisms of vaccine response, and non-response, in autoimmune disease patients, as well as potentially in others taking similar medications. Information may also be uncovered regarding autoimmune disease pathogenesis, predictors of vaccine response, and autoimmune disease flare.

Background IS Medication Testing: A critical part of this study is to discover if withholding cohort-defining IS medications influences response to the additional vaccine dose. In order to determine if there is a correlation between IS medication level in the blood and vaccine response, a whole blood specimen will be collected at the Baseline/Week 0 visit for all participants in Cohorts A (MMF/MPA) and B (MTX). If the primary endpoint analysis yields no quantifiable difference between treatment arms withholding IS medication and those continuing their medication in Cohort A (MMF/MPA) and Cohort B (MTX), the Baseline whole blood and serum specimens will be tested to gain additional insight into a relationship between medication blood levels and vaccine response.

Optional Site-specific Sub-studies: The mechanistic assays noted above represent a small portion of the research that can be completed on autoimmune patients receiving an additional COVID-19 vaccine dose. This study presents a unique opportunity to collect data during a critical time in our vaccine response timeline. Individual site investigators may choose to collect additional optional specimens from Baseline/Week 0 to Week 4 to complete mechanistic analysis of their own. All optional mechanistic specimen sub-studies will be detailed in site-specific informed consent forms.

Optional Week 1 Pediatric Specimen Collection: Pediatric participants may choose to participate in an optional specimen collection during the Week 1 Vaccine Diary Review visit (window: Day 7-14). Procedures for this visit are outlined in Section 20.1 Schedules of Events.

10. Biospecimen Storage

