13.4 Analysis Plan

13.4.1 Analysis Populations

The following populations will be defined separately for Stage 1 and Stage 2.

Vaccinated population: will be defined as all participants who are randomized or allocated and receive study vaccine in the study. For all endpoints, participants will be evaluated by the actual vaccine received. In Cohorts A and B, participants will be analyzed in subgroups defined by randomized assignment to continue or withhold IS medications in the primary analysis.

Per protocol populations: will be defined as the subgroup of participants in the vaccinated population who adhere to the treatment plan for IS medications defined in Section 7.1.1 Protocol-mandated Medications and have no major protocol deviations or ineligible entry criteria that would impact the vaccine response assessment at Week 4.

Safety population: will be defined as all participants who initiate the treatment plan for IS medications or receive an additional dose of vaccine.

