7.3. Measures of Treatment Compliance

The number of participants who receive study vaccine will be summarized by arm.

In study arms that withhold IS medications around the time of vaccination, the total number of days, the number of days prior to vaccine, and the number of days post-vaccine that IS medications are withheld will be summarized.

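### Per-protocol adherence follows a different rule in each randomised plan, and days off drug are summarised by arm for the withhold plan only

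*Protocol*

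**What the plan says.** **Treatment plans (Protocol 7.1.1).** For withhold participants on mycophenolate the rule is: "Participants taking MMF/MPA (any dose) will hold the doses for 3 days before and 10 days after their vaccine dose". Methotrexate is held for at least 7 days before and at least 7 days after vaccination, with a ceiling: "In total, the participant should not hold their MTX for more than 21 days". Neither rule mentions disease activity. Continue participants keep a stable dose over the same window "unless they experience a change in disease activity requiring medication changes".

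**Populations (Protocol 13.4.1, SAP 5).** The per-protocol population is the part of the vaccinated population "who adhere to the treatment plan for IS medications defined in Section 7.1.1 Protocol-mandated Medications", with no major deviation or eligibility failure that would affect the Week 4 response. In the vaccinated population, for Cohorts A and B, "participants will be analyzed in subgroups defined by randomized assignment to continue or withhold IS medications in the primary analysis".

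**Where the per-protocol set is used.** SAP 8.2.3 names it as the sensitivity analysis of the primary analysis. Protocol 13.4.3 and SAP 8.2.4 also repeat the supportive regression models on it, and Protocol 13.4.4 takes the continue-versus-withhold contrast from those models.

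**Adherence reporting (SAP 7.3).** The summary of days held is limited from its first words: "In study arms that withhold IS medications around the time of vaccination, the total number of days" held, and the split before and after vaccine, will be summarised. Nothing equivalent is planned for continue arms.

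**Drug levels (Protocol 9, Background IS Medication Testing).** A baseline sample is taken from everyone in Cohorts A and B, but testing is conditional: "If the primary endpoint analysis yields no quantifiable difference between treatment arms withholding IS medication and those continuing their medication" in those cohorts, the samples are tested.

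**The concern.** A per-protocol comparison of two randomised plans should treat the same post-randomisation event in the same way under both. Here a change to the cohort-defining drug prompted by disease activity is compatible with adherence in one plan and breaks it in the other. The event is foreseeable: Protocol 5.3.1 warns that stopping these drugs may bring on a flare.

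The adherence table is also one-sided. The trial is open-label (Protocol 3.5) and its stated hypothesis is that a temporary stop improves response (Protocol 2). Some participants will have stopped these drugs around earlier doses: "Participants who withheld their IS medications around their initial vaccinations are eligible to participate" (Protocol 4.2.1). Some in the continue arms may do so again. If they do, a small or null effect of withholding is hard to interpret unless the extent is tabulated by arm.

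The drug-level test might have helped, but its trigger refers to a comparison between plans that the primary analysis does not make.

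**Working it through.** **1. The same event under each plan**

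| Event after vaccination, within the hold window | Continue arm | Withhold arm |
|---|---|---|
| Cohort-defining drug changed because of disease activity | Excused by 7.1.1; stays per-protocol | Early restart, not excused; leaves per-protocol |
| Disease activity treated with another permitted drug (Protocol 7.1.2), hold unchanged | Stays | Hold rule still met |
| Drug held or restarted with no disease-activity reason | Leaves | Leaves |

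Only the first row differs. Protocol 8.1.3 narrows it in time: under both plans, active disease at Baseline that leads to more immunosuppression means no vaccine, and hence no place in the vaccinated population. The difference therefore acts mainly in the 10 days (mycophenolate) or 7 days (methotrexate) of required hold after vaccination.

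**2. The plan's own figure for comparing two arms**

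Inputs from Protocol 13.7: 33 evaluable per arm, response 0.25 against 0.584, odds ratio 4.2, power 80%. The alpha for this comparison is not stated there; two-sided 0.05 is assumed.

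- Odds ratio = (0.584/0.416)/(0.25/0.75) = 4.21.
- Standard error under the null, with mean rate 0.417: √(2 × 0.417 × 0.583/33) = 0.1214. Under the alternative: √((0.1875 + 0.2429)/33) = 0.1142.
- Power = Φ((0.334 − 1.96 × 0.1214)/0.1142) = Φ(0.84) = 80.0%. The stated figure reproduces.

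**3. Per-protocol contrast when the plans truly do not differ**

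The documents give no rates, so these are assumed ranges. Let p be the response of participants who do not change drug, f the share who change it for disease activity (equal in both arms) and q their response. Changers are kept in the continue arm and dropped from the withhold arm:

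- continue per-protocol rate = (1 − f)p + fq
- withhold per-protocol rate = p
- apparent gain from withholding = f(p − q)

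Apparent odds ratio for withholding:

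| p | f | q = 0 | q = p/2 | q = p | q = p + 0.20 |
|---|---|---|---|---|---|
| 0.25 | 5% | 1.07 | 1.03 | 1.00 | 0.95 |
| 0.25 | 10% | 1.15 | 1.07 | 1.00 | 0.90 |
| 0.25 | 20% | 1.33 | 1.15 | 1.00 | 0.82 |
| 0.50 | 5% | 1.11 | 1.05 | 1.00 | 0.96 |
| 0.50 | 10% | 1.22 | 1.11 | 1.00 | 0.92 |
| 0.50 | 20% | 1.50 | 1.22 | 1.00 | 0.85 |

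Example: p = 0.50, f = 0.20, q = 0 gives 0.40 against 0.50, a 10-point gap and an odds ratio of (0.5/0.5)/(0.4/0.6) = 1.50. With q = 0.70 the continue rate is 0.54 and the odds ratio is 0.85.

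For q = 0 or p/2 the gap is 0.6 to 10 points. The chance of a false result favouring withholding rises from 2.5% to between 2.9% and 12.5% at 33 per arm, and to between 3.2% and 29.2% at 99 per group (three arms pooled). For q = p + 0.20 the gap is 1 to 4 points the other way. These chances keep the arm sizes fixed and ignore the participants dropped from the withhold arm.

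**4. Self-holding in the continue arm, analysed as randomised**

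Suppose a share h of the continue arm holds the drug and responds at the withhold rate of 0.584. The continue rate becomes (1 − h) × 0.25 + h × 0.584, and the true difference of 0.334 shrinks by the factor 1 − h.

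| h | Continue rate | Power at 33 per arm |
|---|---|---|
| 5% | 0.267 | 75.3% |
| 10% | 0.283 | 70.2% |
| 20% | 0.317 | 59.1% |
| 30% | 0.350 | 47.7% |

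This works against withholding. It is not caused by the per-protocol rule; it shows why the extent of holding in continue arms needs a table.

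**5. What other displays would show**

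SAP 6.3 records immunosuppressive drugs on a dedicated CRF and lists them for all arms, but its table counts a participant once if the drug was ever received, so a short hold does not show there. SAP 7.1 lists deviations and tabulates them overall and by site, not by arm.

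**6. The drug-level trigger**

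Protocol 13.4.2 and 13.6 test each arm alone against 0.25. No plan is compared with another, so the stated condition has no defined result to act on. The comparison exists only in 13.4.4.

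**The case against.** The case for leaving the plan alone has real substance.

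- A reader might infer that the rule favours withholding. The documents do not support that: it holds only if participants who change drug respond worse than the rest, and nothing in either document says so. If the change reduces or stops the drug in a continue participant, the sign may reverse.
- A reader might infer that all flares are removed from the withhold arms. They are not; only an early restart of the held drug breaches 7.1.1.
- A reader might infer that self-holding in continue arms would go unreported. It would appear in the medication listing and as a deviation, and without a disease-activity reason it takes the participant out of the per-protocol set.
- SAP 8.2.3, as a repeat of the single-arm tests, compares no plans, so it yields no biased contrast.
- The window is short, and nothing supports rates as high as 20% within it. The participants known to have stopped their drug did so before randomisation.
- Adult Stage 1 closed on 15 August 2022, so a change to conduct could reach only Pediatric Stage 1. The SAP summarises protocol Version 3.0, expects updating, and defers detail of the supportive analyses.
- An early restart is a move to the comparator condition, while an adjusted dose in a continue participant may not be. Counting both as adherent would put crossovers into the per-protocol set.

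All of this limits the point, but the asymmetry remains in the replicated contrast. The last argument bears on which common rule to choose, not on whether to have one. Deferred detail is also the easiest place to settle it.

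**Conclusion.** The point stands as a modest, inexpensive correction. Among the randomised arms, a drug change for disease activity is excused under one plan only, and the per-protocol set inherits this by reference. The per-protocol replication of the continue-versus-withhold contrast can therefore be biased, with a sign the documents do not determine: apparent odds ratios from 0.82 to 1.50 under no true effect, on assumed shares of 5% to 20% and assumed responses. Smaller shares give proportionally smaller gaps. The primary analysis, in the vaccinated population by randomised plan, is unaffected.

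The reporting gap is narrower than silence: what is missing is a planned by-arm summary of days off drug in the continue arms. The drug-level trigger cannot be applied as written, and a baseline sample could not show holding after vaccination in any case.

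**What to change.** 1. In Protocol 13.4.1 and SAP 5, state one rule for both randomised plans when the cohort-defining drug is changed for disease activity within the hold window, for example excluding such participants from the per-protocol set under both. This removes the artefact in step 3 fully only if the share changing drug and their response are the same in both arms; the set is still selected after randomisation.
2. In SAP 7.3, summarise days without the cohort-defining drug, before and after vaccination, for every Cohort A and B arm, using the Immunosuppressive Medication CRF.
3. In Protocol 9, tie the stored-sample drug-level test to the continue-versus-withhold contrast of 13.4.4.
4. The sponsor should reconcile Protocol 7.1.1 with 7.3 (access to medically necessary care) and 8.1.3 (immediate restart stated only for those not vaccinated) on disease activity after vaccination in withhold participants. No clinical rule is proposed here.

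The cost is wording in two documents and one wider table from data already collected. With the example rule the per-protocol set becomes slightly smaller.

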7.1.2 Other permitted concomitant medications

Other than the prohibited medications listed in Section 7.3 Prohibited Medications, treatment with concomitant medications for treatment of SLE, RA, MS, pemphigus, and SSc in adult participants and JIA, JDM, pediatric SLE, and POMS in pediatric participants is permitted throughout study participation. Permitted concomitant medications include B cell modulating therapies such as epratuzumab (anti-CD22, modulates B cell signaling) or agents that target B-lymphocyte stimulator (BlyS; belimumab, atacicept), but these agents are not considered to be BCDT for defining assignment to Cohort C.

Concomitant therapies taken for the long-term treatment of pre-existing conditions other than SLE, RA, MS, pemphigus, and SSc should be continued during the study, provided that they are in accordance with the exclusion criteria. Other permitted concomitant medications may not change between Randomization/Allocation and the Baseline/Week 0 visit. This includes the addition of new medications, or changes in dose and/or frequency of existing medications.

7.2 Prophylactic Medications

Female participants of childbearing potential will be counseled to use an effective method of contraception (e.g., total abstinence, oral contraceptives, intrauterine devices, barrier method with spermicide, surgical sterilization or surgically sterilized partner, medroxyprogesterone acetate, levonorgestrel implant, etonogestrel/ethynodiol vaginal ring, or hormonal implants) for the duration of study participation.

7.3 Prohibited Medications

All participants are to have access to any care deemed medically necessary, but administering the following medications, for the purposes of this study, are prohibited and will be considered protocol deviations unless otherwise noted.

- Any SARS-CoV-2 vaccine administered outside of the study is prohibited.
- All other vaccines administered outside of the study are prohibited between Screening and Week 4 during Stage 1 participation and between Screening and Week 4 during Stage 2 participation.
- Other vaccines, including the flu vaccine, administered within 4 weeks prior to a study visit, starting with the Baseline visit.
- Intravenous or subcutaneously administered immune globulin within 4 weeks prior to a study visit
- Monoclonal antibodies for pre-exposure prophylaxis are prohibited between Screening and Week 4 during Stage 1 participation and between Screening and Week 4 during Stage 2 participation.

If a participant takes a prohibited medication during the study, it should be recorded as a protocol deviation in the eCRF. Participants who received a SARS-CoV-2 vaccine outside of the study will be withdrawn. All other participants will continue to be followed for safety.

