11.2 Participant Stopping Rules and Withdrawal Criteria

Participants may be prematurely terminated from the study for the following reasons:

1. The participant and/or legal guardian elects to withdraw consent from all future study activities, including follow-up.
2. The participant is "lost to follow-up" (i.e., no further follow-up is possible because attempts to reestablish contact with the participant have failed).
3. The participant dies.
4. The Investigator no longer believes participation is in the best interest of the participant.
5. The participant does not receive the additional vaccine dose at Baseline/Week 0 or S2 Baseline/Week 0 (new recruits only) for any reason, including the criteria listed in Section 8.1.3 Baseline (Week 0/Day 1) Visit or at Section 8.2.4 Baseline (Week 0/Day 1) Visit, respectively.
6. The participant receives a SARS-CoV-2 vaccine outside of the study.

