11.3 Participant Replacement

Participants who withdraw or are withdrawn will not be replaced if they have received a vaccine dose at a given stage of the study. If a Stage 1 or newly recruited Stage 2 participant is randomized or allocated to a study arm but does not receive the vaccine, the participant will be withdrawn and will not be counted toward the total accrual objective. If a Stage 2 rollover patient is allocated to a study arm but does not receive the vaccine, the participant will continue on their previous Schedule of Events and will not be counted toward the Stage 2 accrual objective. Additional participants will be consented and randomized/allocated to achieve the accrual objective(s).

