12.4.2 Increase in Autoimmune Disease Activity

Any increase in autoimmune disease activity (flare/relapse) for the participant's qualifying autoimmune disease will not be reported as an AE. These events will be collected and reported on the disease-specific assessment eCRFs. (Section 8.1.4.2 Disease-Specific Assessments).

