13.4.2 Primary Analysis of Primary Endpoint

The primary endpoint of a protective antibody response will be the proportion of participants who reach the laboratory-defined threshold for the NIAID-VRC MSD 3 plex (Wu-1 full-length spike, RBD, and N proteins) assay. Participants with missing Week 4 anti-COVID-19 antibody response data with a documented COVID infection will be considered as not having a protective antibody response. All other participants missing Week 4 anti-COVID-19 antibody response data will be considered to be missing-completely-at-random (MCAR). Intercurrent events which result in Week 4 anti-COVID-19 antibody response data being unevaluable for immune response, including receipt of monoclonal antibodies or plasma products directed against SARS-CoV-2 and any SARS-CoV-2 vaccine outside of the study, will also result in data being considered to be missing-completely-at-random (MCAR).

The primary analysis will be evaluated independently within each arm (defined by age, cohort, vaccine, and IS treatment plan) and within subgroups with either a negative or suboptimal response to prior vaccines (defined as Roche Elecsys® Anti-SARS-CoV-2 S result \leq 200 U/mL) or with a low immune response (defined as Roche Elecsys® Anti-SARS-CoV-2 S result $>$ 200 U/mL and \leq 2500 U/mL). The primary analysis will be performed in the vaccinated population. The proportion of participants meeting a protective antibody response criteria will be reported in each arm and subgroup with 90% Clopper-Pearson confidence intervals and analyzed using a one-sided exact test with alpha = 0.05 against the null hypothesis that the probability of achieving a protective immune response is \leq 0.25. P-values will not be adjusted for

multiple comparisons. The primary analysis will also be conducted in the subgroup of participants with a Roche Elecsys® Anti-SARS-CoV-2 S result ≤ 50 U/mL at the Screening visit. Each analysis will occur after the evaluable participants assigned to that arm have completed the Week 4 study visit or are withdrawn from the study.

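### Protocol 7.3 ends safety follow-up after any outside SARS-CoV-2 vaccine dose, so the 12-week flare and 24-week SAE windows behind the DSMB triggers can close early; the effect is probably modest

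*Protocol*

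**What the plan says.** **The rule.** Protocol 7.3 states: "Any SARS-CoV-2 vaccine administered outside of the study is prohibited". It sets no end date. The ban on prophylactic antibodies does have one: "Monoclonal antibodies for pre-exposure prophylaxis are prohibited between Screening and Week 4 during Stage 1 participation", with the same limit in Stage 2. The consequence of an outside dose is then given: "Participants who received a SARS-CoV-2 vaccine outside of the study will be withdrawn. All other participants will continue to be followed for safety". Section 11.2 item 6 names the same event, "The participant receives a SARS-CoV-2 vaccine outside of the study", but its lead-in only permits termination. The two sections therefore differ in force.

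**After withdrawal.** Section 8.1.6 asks sites to request an Early Termination Visit. The Early Termination column of the schedules in 20.1 marks the disease and flare assessments. Section 11.4 allows, but does not require, a final phone visit on adverse events and concomitant medication. Pregnancy is the only thing the protocol says it will go on monitoring. On replacement, 11.3 says: "Participants who withdraw or are withdrawn will not be replaced if they have received a vaccine dose at a given stage of the study".

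**What is collected, and for how long.** Under 12.4.1, SAEs, MAAEs, NOCMCs, AESIs and COVID-19 diagnoses are collected to the end of the individual's participation. In Sanofi-GSK arms the AESIs include new potential immune-mediated diseases (pIMDs). Under 12.4.2, a flare of the participant's "qualifying autoimmune disease will not be reported as an AE". Instead, "These events will be collected and reported on the disease-specific assessment eCRFs".

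**The triggers.** Section 12.8.2.2 calls an ad hoc DSMB review for severe flare within 12 weeks of vaccination in 3 of the first 10 participants, or 30% thereafter. It also does so for 3 or more vaccine-related Grade 3 or higher SAEs of the same type. SAEs count within 24 weeks in adults and up to the Week 24 visit in children.

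**The concern.** The ban lasts for the whole of participation, but the safety windows run 12 and 24 weeks. A participant who takes a community dose inside either window leaves observation before it closes, and nothing in the protocol carries the window past withdrawal. If only the phone call takes place, flares of the qualifying disease need not be recorded, because they are not adverse events.

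Three things could suffer. The flare count behind the 30% trigger could be too low. Vaccine-related SAEs between withdrawal and Week 24 could be missed. Late pIMDs could go unrecorded after a vaccine that Protocol 1.1 describes as not yet used in autoimmune disease.

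The event is foreseeable: SAP 6.3 plans to tabulate SARS-CoV-2 vaccines received outside the study.

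**Working it through.** The plan states no figure on this point, so there is none to reproduce. The check has three parts.

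**1. Window coverage per participant.** Inputs: flare window 12 weeks and SAE window 24 weeks (12.8.2.2); follow-up 48 weeks with clinic visits at Weeks 4, 12, 24, 36 and 48 (3.1). For withdrawal just after week *t*, coverage is min(*t*, 12)/12 and min(*t*, 24)/24, and weeks lost are 48 − *t*.

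| Withdrawn just after | Flare window observed | SAE window observed | Weeks lost | Visits lost |
|---|---|---|---|---|
| Week 4 | 4/12 = 33% | 4/24 = 17% | 44 | 4 of 5 |
| Week 8 | 8/12 = 67% | 8/24 = 33% | 40 | 4 of 5 |
| Week 12 | complete | 12/24 = 50% | 36 | 3 of 5 |
| Week 24 | complete | complete | 24 | 2 of 5 |

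An Early Termination Visit recovers events up to its own date. The 7-day solicited events, the Day 28 unsolicited events and the 6-week myocarditis/pericarditis trigger are untouched if withdrawal comes after them.

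**2. Effect on the 30% flare trigger.** Assumptions: true 12-week severe-flare risk 30%; constant hazard; withdrawal unrelated to flare; flares up to withdrawal are captured; withdrawn participants stay in the denominator (12.8.2.2 does not say). The share withdrawn, *w*, is set at 5%, 10% and 20%, because the documents give no rate.

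- Risk by Week 4: 1 − 0.7^(4/12) = 11.2%. Risk by Week 8: 1 − 0.7^(8/12) = 21.2%.
- Observed rate = 0.30(1 − *w*) + (risk by withdrawal) × *w*.
- All withdrawn at Week 4: 29.1%, 28.1%, 26.2%.
- All withdrawn at Week 8: 29.6%, 29.1%, 28.2%.

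With flare and withdrawal times both uniform over the 12 weeks, the observed rate is 0.30(1 − *w*/2). That is 29.3%, 28.5%, 27.0% and 25.5% for *w* = 5%, 10%, 20% and 30%. For a single look at 40 vaccinated participants with a true rate of 35%, the binomial chance of seeing at least 12 (30%) is 79.5% with no withdrawals. It falls to 76.0%, 72.3%, 63.9% and 54.6% for the same four values of *w*.

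Two limits on these figures. If withdrawn participants left both numerator and denominator, the dilution would vanish under the same independence assumption, and only the number observed would fall. If a Week 8 withdrawal led only to a phone call, flares after the Week 4 visit could be missed, and the Week 8 results would move toward the Week 4 results.

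**3. Who is still affected under version 7.0 (13 December 2022).** Adult Stage 1 closed to enrollment on 15 August 2022, and vaccination must fall within 28 days of Screening (8.1.3). Taking the closing date as the last possible Screening date, the last vaccination is 12 September 2022. The last 12-week flare window then ends on 5 December 2022, before version 7.0. The last 24-week SAE window ends on 27 February 2023. The flare point therefore applies to Adult Stage 2 and both pediatric stages.

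**The case against.** The strongest defence is attribution. An outside SARS-CoV-2 vaccine is the same kind of exposure as the study product, so it competes as a cause of SAEs, pIMDs and flares. Section 12.3.2 attributes events to the study-provided vaccine, the SAE trigger counts only vaccine-related events, and the synopsis limits the triggers to events attributable to the vaccine. Weeks after an outside dose are contaminated weeks. This stands as a cost, but it argues for reporting those weeks separately rather than not observing them. Rollover participants also leave their Stage 1 follow-up at the next dose, yet they stay under observation from a new Day 1. Outside-vaccine recipients do not.

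The Early Termination Visit also counts for the plan. It is more than a formality, since it includes the flare assessments, and it may be combined with the phone call. What is lost is the time after that visit. The DSMB meets about every 6 months and can be called at any time, but it sees only what has been collected. Section 12.5.1 speaks of reporting certain events until the end of the study. The collection period in 12.4.1 is the participant's own participation, so that wording does not restore follow-up.

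Two stronger readings are tempting. A reader might infer that the protocol contradicts itself by keeping monoclonal-antibody recipients in follow-up, since 13.4.2 groups "receipt of monoclonal antibodies or plasma products directed against SARS-CoV-2 and any SARS-CoV-2 vaccine outside of the study" as one kind of intercurrent event. That grouping concerns whether the Week 4 titre can be evaluated. It says nothing about safety attribution, where a second vaccine dose differs from an antibody. A reader might also infer from 4.1 that the study sends enrolled participants for community bivalent doses and then withdraws them. Section 4.1 is a rationale for the study population, the protocol also calls pre-screening candidates participants (8.1.2.1), and the text does not say which group is meant. The point does not rest on either reading.

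**Conclusion.** The concern holds as an optional improvement. Section 7.3 makes withdrawal mandatory at any time and reserves continued safety follow-up for everyone else, while 11.2 item 6 only permits termination. An outside dose before Week 12 or Week 24 cuts short the flare or SAE window behind a DSMB trigger, and pIMD collection in Sanofi-GSK arms stops.

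The size is probably modest: 0.4 to 3.8 percentage points off a true 30% flare rate in the Week 4 and Week 8 scenarios. That range rests on assumed withdrawal shares of 5% to 20% and on keeping withdrawn participants in the denominator.

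A reader might infer that the DSMB triggers are disabled or that the efficacy results are biased. The documents do not support that. The 30% figure prompts a review and is not a statistical test, and 13.4.2 already has a rule for Week 4 titres after an outside dose. Confidence is high on what the text says and low on how often the event occurs.

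**What to change.** Reword 7.3 and 11.2 item 6 so that they agree:

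- An outside SARS-CoV-2 dose ends evaluability for antibody endpoints. Later titres are flagged or excluded. Section 13.4.4 already leaves this handling to the SAP, and SAP 8.3.3 is still open on it.
- The participant stays on the scheduled safety and flare assessments at least through the Week 12 and Week 24 windows, and preferably to Week 48.
- Events after the outside dose are tabulated separately by arm.

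It would help to state in 12.8.2.2 whether withdrawn participants stay in the flare denominator.

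The cost is a wording change in two protocol sections and one split safety table in the SAP, with no new procedure, endpoint or sample size. The downsides are that events after the outside dose are harder to attribute to the study vaccine, and that sites run scheduled visits that withdrawal would have ended.
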